3 OBJECTIVES AND ENDPOINTS

OBJECTIVES	ENDPOINTS	JUSTIFICATION FOR ENDPOINTS
Primary		

 Determine the safety and tolerability of a singly applied NB01 Define engraftment of a singly applied topical NB01 Dose schedule determination based on engraftment 	
Safety Assessments:
 
 Skin Dryness Skin Peeling Irritant/Contact dermatitis Hyperpigmentation Ocular Toxicity Mucosal Toxicity Skin erythema Assessment of Disease Status 
Efficacy Assessments: Engraftment is defined as deoR/PanBac>40% and Cas5/PanBac>40%. Disease associated bacteria are typically deoR, Cas5 negative (Kang et al, 2016), therefore, ratios are expected to be low <10% in acne subjects. The NB01 strain as measured with our TaqMan assays is approximately 100% deoR/PanBac and Cas5/PanBac, so we expect the ratio to increase with successful engraftment. This will help to determine dosing regimen/schedule for multi-dosed trials where the drug will be applied in a frequency to ensure that product levels remain above these parameters. For example, if deoR/PanBac drops to <40% at or before 6 hours then the application will be twice daily (BID); every (Q) 12 hours.
	Disease exacerbation along with erythema, dryness, pigmentation irritant/contact dermatitis, mucosal and ocular toxicity are commonly tested safety endpoints in topical dermatologic trials.
Secondary		
To evaluate clinical efficacy using IGA and acne lesion counts of a singly applied NB01	IGA and acne lesion count	IGA and acne lesion counts are conventional measurements for assessing efficacy in acne trials
Tertiary/Exploratory		
To evaluate biomarkers of	
 Porphyryn and sebum levels 	Porphyryn is a known

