We aim to test this in a Phase Ib single application study evaluating the safety, tolerability, and clinical impact that a single application of NB01 has on adult subjects with moderate acne. We want to profile the change in microbiome over the course of therapy to determine if exogenously delivered bacteria can populate the skin (engraftment) and cause a shift in the microbiome safely and subsequently impact acne biomarkers (porphyrin) that may correlate with clinical disease. Health-associated *P. acnes* contain both deoR and Cas5, thus the ratios of deoR/PanBac and Cas5/PanBac is approximately 1 in our formulation. Disease associated *P. acnes* typically lack deoR and Cas 5 (Kang et al, 2016) leading to a deoR/PanBac <10% on acne individuals. We expect an upwards shift in deoR/PanBac and Cas5/Panbac with the application of our strains to acne subjects. Thus, engraftment is defined as deoR/PanBac>40% and Cas5/PanBac>40%. This will help to determine dosing regimen/schedule for multi-dosed trials where the drug will be applied in a frequency to ensure that product levels remain above these parameters. For example, if deoR/PanBac drops to <40% at or before 6 hours then the application will be BID (Q12 hours). Disease-associated strains, in contrast, typically lack deoR and Cas4, but contain transposase2 (TPase2). Subjects will also be profiled with TPase2/PanBac ratios to determine how the pathogenic strain profiles are impacted over time with application of drug, and if there are certain profiles that increase or decrease likelihood of successful engraftment.

Engraftment measurements would be more challenging to obtain in healthy individuals in which we would be trying to replace a healthy microbiome with a healthy microbiome. Our product is low risk, using bacteria native not only to human skin, but to the pilosebaceous units of the face, and *P. acnes* makes up 90% of the bacteria on the skin in both diseased and healthy individuals (Fitz-Gibbon et al. 2013).

We intend for this therapy to eventually be used in all ages of acne subjects ranging from 13-40, and all disease severities as either monotherapy for mild to mild/moderate acne and as an adjuvant therapy for moderate to severe acne at all body sites, with special attention to facial involvement.

This approach is standard to acne therapy whereby mild disease will be treated with a monotherapy (i.e., 5.0% BPO) and moderate/severe disease will be treated with various combinatory regimens (topical

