4.3 JUSTIFICATION FOR DOSE

P. acnes is normal, commensal bacteria on the facial skin and within the facial pilosebaceous units. *P. acnes* species make up around 90% of the bacterial species on the face, irrespective of health or disease states (Fitz-Gibbon et al. 2013), (Tomida et al. 2013). In administering our live microbiome transplant topically to the face, we are delivering our health-associated *P. acnes* strains directly into their native niche, enabling optimal engraftment and thereby any beneficial effect of restoring a microbiome population to a healthy profile.

Dose Justification:

- Lower-bound dose of 10^5 CFU/cm² determined using the average within the range of normal bacterial concentration for facial skin (10^4 - 10^7 CFU/cm²) (Kishishita et al. 1980), (Akaza et al. 2016), (Nakatsuji et al. 2017) (http://www.textbookofbacteriology.net/normalflora_3.html)
- Upper-bound dose of 10^6 CFU/cm² determined by using the upper limit of normal bacterial concentration for facial skin.

Further rationale to the study design of performing topical microbiome transplants with our dose can be extracted from the methods in (Nakatsuji et al. 2017) which studied autologous microbiome transplants of 10^5 CFU/cm² CoNS in atopic dermatitis subjects.

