6 STUDY INTERVENTION

6.1 STUDY INTERVENTION(S) ADMINISTRATION

6.1.1 DOSING AND ADMINISTRATION

There will be a single application of NB01, at 1 of 2 dose cohorts, administered to approximately 10 subjects:

Once a subject has completed BPO pre-treatment (with an in-home patient e-diary) and been enrolled into the trial, the subject will provide a post-BPO sample immediately prior to receiving their application of NB01 (hereafter referred to as “study drug”). The PI will apply a single dose of NB01 at one of two strengths to each subject at time point 0 hours (0H):

- Cohort 1: Initially, 5 subjects will be enrolled to receive a single topical application of NB01 at 10^5 CFU/cm² to 50 cm² of facial skin covering the nose and cheek. The lower-bound dose determined using the average range of normal bacterial concentration for facial skin (10^5 CFU/cm²).
- Cohort 2: If there are less than 2 DLTs in Cohort 1, then 5 subjects will have a single topical application of NB01 at 10^6 CFU/cm² to 50 cm² of facial skin covering the nose and cheek. The upper-bound dose was determined by upper limit of normal bacterial concentration for facial skin (10^6 CFU/cm²).

Investigators applying the drug shall wash their hands and wear non-powdered nitrile gloves for application of study drug material. Subjects will wash their face with Cetaphil® right after the time point 0H engraftment sample procurement and just before the study drug application. Subjects will document their BID Cetaphil® washing for the remainder of the study.

See Study Assessments and Procedures, for details on pre-and post-visit requirements during the treatment period.

See the Pharmacy Manual for additional study drug handling and management details for this study.

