Post BPO-period porphyrin level, sebum production, pH, IGA assessment, total lesion count, and photos will be obtained on Day 1, followed by the engraftment assay. Urine dipstick pregnancy test will be obtained for females of childbearing potential. After these measurements are obtained, subjects will wash their face with Cetaphil® (Galderma) in the office and then the single study drug dose will be applied by the PI (OH). The application should take place at least 24 hours after the last morning BPO application. The PI will apply drug once (time point 0H) to the face: cheek/nose (approximately 50 cm²) to Cohort 1 subjects. If there are less than 2 DLTs and no possibly-related SAEs in Cohort 1 during the 7-day safety assessment, the remaining subjects will be enrolled into Cohort 2 to receive single application to the face: cheek/nose. Subjects will then be monitored for at least 30 minutes after the application for any allergic or anaphylactic reactions. Subjects should not wash or shave their face again until the 24H sampling is completed with the exception that the Bioré® strip follicular assessment will be obtained after washing face with Cetaphil® in office. Subjects may then initiate facial cleansing with Cetaphil® wash BID. However, for all office visit days, subjects should hold the morning wash and morning shaving until visit samples have been obtained.

Engraftment sample procurement: Samples for engraftment will be obtained using a Fab-Swab Filtered Air Breathable Sterile Flocked Collection Device (PurFlock® Ultra-Puritan Diagnostics). The face will be quartered into left lateral, left medial, right lateral, right medial for sampling procurement, with mid pupillary line splitting medial and lateral quarters and midline forehead/nose splitting medial quarters. Each sampling will only test a quarter of the face to ensure that sampling post drug application do not remove study drug prior to the next sampling time point and to improve standardization of sampling area. To obtain samples, the swabs should be pressed firmly and rubbed over the designated quadrant for that sample time-point with occasional rotation of the swab for a duration of a minimum of 30 seconds. Please refer to the Laboratory Manual for detailed instructions.

Subjects will be monitored for safety at all study visits: 0H, 6H, 24H, 48H, 7 days and 28 days after the initial application.

Vitals will be taken at study visits: Screening, 24H, 7 days, and 28 days.

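### The engraftment definition names no time point or wash condition, so the pre-wash 6H and 24H swabs can exceed 40% on residual product alone

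*Combined protocol and SAP*

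**What the plan says.** Section 3 sets the primary engraftment endpoint: "Engraftment is defined as deoR/PanBac>40% and Cas5/PanBac>40" per cent. Section 4.2 repeats the thresholds and gives the purpose, which is "to determine if exogenously delivered bacteria can populate the skin (engraftment"). Neither section says at which visit the ratio is to be read, whether it must survive a wash, or whether it must persist. Section 10.4.1 adds no engraftment time point or responder rule.

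On the assay, section 3 says "The NB01 strain as measured with our TaqMan assays is approximately 100% deoR/PanBac and Cas5/PanBac", while for resident flora "ratios are expected to be low <10% in acne subjects".

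Cheek swabs are scheduled at Screening, 0H, 6H, 24H, 48H, Day 7 and Day 28 (section 1.2). The face is washed just before dosing. After that, section 8.1 says "Subjects should not wash or shave their face again until the 24H sampling is completed"; the one exception is the 24H Bioré strip, which follows an office wash. Footnote m of the schedule agrees: twice-daily washing starts at 24H, and on clinic days sampling comes before washing.

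Section 3 also uses the ratio for the third primary objective, dose-schedule determination. There it treats the ratio as a level of product and gives a worked example tied to the reading at or before 6 hours.

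**The concern.** Populating the skin and still lying on the skin are different states, and a ratio read before any wash does not separate them. A product that is about 100% positive on both markers raises both ratios simply by being applied, and does so even if both were 0% at 0H. Section 2.1 says BPO pre-treatment is there to lower the resident load, which makes the denominator easier to dominate.

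Two of the five post-application swabs (6H and 24H) fall in this window. If they are read against the stated threshold, the second primary objective (define engraftment) could be answered in the affirmative by application itself. An early comparison between cohorts could likewise reflect the tenfold difference in deposited dose. With about five subjects per cohort, open label and no formal hypothesis, an advance statement of which reading counts is the main safeguard against choosing a favourable one later.

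**Working it through.** The plan gives no calculation for this endpoint, so there is no figure to reproduce. The check asks what ratio the deposit alone would produce.

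**Inputs from the documents**
- Dose D: 10^5 CFU/cm² in Cohort 1 and 10^6 in Cohort 2 (section 6.1.1). The low-dose cohort receives a "single topical application of NB01 at 10^5 CFU/cm² to 50 cm² of facial skin covering the nose and cheek".
- Marker share of the product: about 100% (section 3).
- Marker share of resident flora, b: below 10% (section 3); 0 to 10% is used here.
- Resident load R: the protocol's "range of normal bacterial concentration for facial skin (10^4 - 10^7 CFU/cm²"), with 10^5 described as average (sections 4.3 and 6.1.1).

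**Assumptions, not in the documents**
- R after BPO is taken across the protocol's own range.
- The retained fraction of the deposit, s, is 1 unless stated.
- There is no growth, only dosed skin is swabbed, and marker signal is proportional to CFU.

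**Formula**

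Ratio = (sD + bR) / (sD + R)

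This exceeds 0.40 when 0.6·sD > (0.4 − b)·R, that is, when sD/R > (0.4 − b)/0.6.
- b = 0: sD/R > 0.67, so R < 1.5·sD
- b = 0.10: sD/R > 0.50, so R < 2.0·sD

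**Ratio from the deposit alone at full retention (b = 0 to b = 0.10)**

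| R (CFU/cm²) | Low dose, 10^5 | High dose, 10^6 |
|---|---|---|
| 10^4 | 91–92% | 99% |
| 10^5 | 50–55% | 91–92% |
| 10^6 | 9–18% | 50–55% |
| 10^7 | 1–11% | 9–18% |

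Example: low dose, R = 10^5, b = 0.10 gives (100,000 + 10,000)/(100,000 + 100,000) = 0.55. Five of the eight cells pass and three fail.

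**Retention needed to pass, s = (0.4 − b)/0.6 × R/D**

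| R (CFU/cm²) | Low dose | High dose |
|---|---|---|
| 10^4 | 5–7% | 0.5–0.7% |
| 10^5 | 50–67% | 5–7% |
| 10^6 | not possible | 50–67% |
| 10^7 | not possible | not possible |

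**Comparison between cohorts.** At full retention the deposit alone puts both cohorts on the same side of 40% at R = 10^4, 10^5 and 10^7, and separates them only at 10^6. With 10% retention it separates them at R = 10^5 (9–18% against 50–55%).

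**The case against.** The strongest reply is that nothing in the plan says a subject above 40% at 6H or 24H will be declared engrafted. A reader might infer an any-time responder rule from the bare definition, but none is written. Section 10.4.1 tabulates every subject at every time point and plots primary outcomes over time, so a subject at 90% at 6H and 5% at 48H would be visible. That stands: the gap is in what the term means and which reading carries it, not in the data collected.

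A reader might also infer that residual product is bound to pass, or that the higher dose is bound to look better engrafted. The documents support neither. Post-BPO load and retention are not stated, three of the eight cells fail even at full retention, and swabbed quarters extending beyond the roughly 50 cm² dosed area would dilute the ratio. The cohorts separate on the 40% criterion only for some loads and retentions.

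The early readings also have a stated purpose. The title refers to short-term engraftment, section 8.1 stresses timing at 6H, 24H and 48H, and the dose-schedule objective uses the ratio as a measure of product on the skin. That is a good reason to keep the early swabs. It does not make a pre-wash reading evidence that bacteria have populated the skin.

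Finally, the 24H Bioré strip already gives a post-wash follicular measure, and three later swabs follow washing. Both points are correct, but the definition does not call on any of these samples. That the 24H swab precedes the strip wash is implied by section 8.1 and footnote m rather than spelled out, and the Laboratory Manual was not available.

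**Conclusion.** The concern holds as a possibility. The definition names no time point or wash condition, and at the protocol's own average resident load of 10^5 CFU/cm² undiminished deposit alone would read 50–55% at the low dose and 91–92% at the high dose. A positive 6H or 24H swab therefore cannot by itself distinguish residual product from populated skin.

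The size depends on post-BPO load and retention, neither of which is documented, and on the no-growth and dosed-skin-only assumptions. If the resident load stays at 10^6 or above, deposit alone does not pass at the low dose; at 10^7 it passes at neither. Confidence is moderate.

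**What to change.** Keep both 40% thresholds and every sample, and change the wording in sections 3, 4.2 and 10.4.1, with the matching objective in the synopsis:

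- Report the 6H and 24H cheek swabs as product retention before washing, and keep them for the product-level use under the dose-schedule objective.
- Reserve the term engraftment, and any between-cohort statement about it, for post-wash samples. The 48H swab is the earliest swab readout, supported by persistence at Day 7 and Day 28; the post-wash 24H Bioré strip is the early follicular readout.
- State that 48H reduces carry-over but does not exclude it. At R = 10^4, retaining about 5–7% of the low-dose deposit or 0.5–0.7% of the high-dose deposit would still pass, and nothing in the documents shows that washing between 24H and 48H removes more than that. This is why Day 7 and Day 28 are needed alongside it.
- Reconcile the dose-schedule objective, which is said to rest on engraftment, and its 6-hour example with the new label. No dosing rule is proposed here.
- State explicitly that the 24H cheek swab is taken before the office wash for the strip.

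The cost is wording only, with no new visit or sample. The downside is that fewer time points, and probably fewer subjects, will count as engrafted.

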Recent literature from the Human Microbiome Project has shown there are unique microbial signatures specific to healthy and acne disease states (Fitz-Gibbon et al. 2013), (Tomida et al. 2013). Subsequent literature discovered a repressor in the porphyrin pathway in health-associated strains resulting in significantly lower porphyrin production (Johnson et al. 2016). Porphyrin is a known inflammatory mediator in acne pathogenesis (Kang et al. 2015). Porphyrin levels inversely correlate with therapeutic improvement in acne. (Richter et al. 2016). Additional papers have highlighted other virulent factors such as the pIMPLE plasmid that may be associated with acne pathogenesis and were found to be more common in disease-associated strains (Kasimatis et al. 2013).

From this data, we hypothesize that by eliminating resident disease-associated bacterial strains and replacing them with a health-associated *P. acnes* transplant, we may be able to improve, mitigate, treat, or prevent acne flares. We aim to test this in an initial Phase I evaluating the safety, tolerability, and clinical impact that a single dose application of NB01 has on adult subjects with moderate acne.

This initial study will be a Phase Ib single center open label dose escalation study using a single dose application with monitoring over 28 days on 10 subjects at 2 different concentrations (lower bound and upper bound). If we meet the safety criteria of this initial study, we plan to expand the IND research to a Phase Ib multi-dosed study. All subjects will be pre-treated with a daily 5.0% BPO gel (<https://www.perrigo.com/business/product.aspx?ID=88&let=B> Perrigo 5% BP Aqueous Gel) to decrease their resident microbiome bacterial load in preparation for transplantation and successful repopulation with a healthy microbiome.

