6.2.4 PREPARATION

Study Drug Application:

Study drug should be removed from freezer 15 minutes prior to application and allowed to thaw at room temperature.

Subjects' dose will be PI-administered at 0H study visit after samples have been procured for engraftment assay. Administers of study drug should wash their hands and wear non-powdered nitrile gloves for application. Subjects will wash their face with Cetaphil® right before in-office application, on Day 1.

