9 EFFICACY

9.1 CONSIDERATIONS FOR EFFICACY

- **Tolerability Scale for Topical Acne Treatments, all visits:**

Reference: ClinTrials.gov: [Investigator Assessment Tolerability Scoring: A Study to Evaluate Tolerability of Two Topical Drug Products in the Treatment of Acne](#). Please see Appendix C of this protocol.

1. Skin Dryness Score: Investigator Assessment of Tolerability Scale (0 = None; 1 = Slight; 2 = Moderate; 3 = Intense)
2. Skin Peeling Score: Investigator Assessment of Tolerability Scale (0 = None; 1 = Slight; 2 = Moderate; 3 = Intense)
3. Irritant/Allergic Contact Dermatitis Score: Investigator Assessment of Tolerability Scale (0 = None; 1 = Slight; 2 = Moderate; 3 = Intense)
4. Hyperpigmentation Score: Investigator Assessment of Tolerability Scale (0 = None; 1 = Slight; 2 = Moderate; 3 = Intense)
5. Ocular Irritation: Investigator Assessment of Tolerability Scale (0 = None; 1 = Slight; 2 = Moderate; 3 = Intense)

6. Conjunctival Injection: Investigator Assessment of Tolerability Scale (0 = None; 1 = Slight; 2 = Moderate; 3 = Intense)
 7. Mucosal Toxicity: Investigator Assessment of Tolerability Scale (0 = None; 1 = Slight; 2 = Moderate; 3 = Intense)
 8. Skin Erythema Score: Investigator Assessment of Tolerability Scale (0 = None; 1 = Slight; 2 = Moderate; 3 = Intense)
- **Assessment of disease status using IGA Score and Acne Lesion Count**
 - **Engraftment and Dose Schedule Determination**

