10.4 STATISTICAL ANALYSES

10.4.1. GENERAL APPROACH

Data will be tabulated and summarized for each subject at each time point. In addition, data for all variables will be summarized using descriptive statistics overall and by each dose cohort separately. Primary endpoints for safety will be summarized using means and standard deviation for continuous variables and frequencies and percentages for categorical variables. Plots of primary outcomes will be produced examining trends over time. Subject trajectories will be plotted for Secondary and Exploratory endpoints using spaghetti plots and changes over time in the IGA and acne lesion count will be summarized. Correlation between the efficacy biomarkers overall and by cohort and time point will be examined for changes and trends.

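### The example dosing rule (below 40% by 6 h, so dose every 12 h) conflicts with the stated aim of staying above 40%, and one swab pattern leaves 12-hourly dosing undecided

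*Combined protocol and SAP*

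**What the plan says.** Dose schedule determination from engraftment is the third primary objective (Sections 1.1 and 3). Engraftment requires two ratios, deoR/PanBac and Cas5/PanBac, both above 40%. For the later multi-dosed trials, Section 3 states the aim that "the drug will be applied in a frequency to ensure that product levels remain above these parameters". The example follows directly: "For example, if deoR/PanBac drops to <40% at or before 6 hours then the application will be twice daily (BID); every (Q) 12 hours". Section 4.2 repeats the aim and the example: "if deoR/PanBac drops to <40% at or before 6 hours then the application will be BID (Q12 hours").

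No other rule appears. Section 9.1 carries only the line "Engraftment and Dose Schedule Determination". Section 10.4.1 is descriptive: "Data will be tabulated and summarized for each subject at each time point".

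The dose is "PI-administered at 0H study visit after samples have been procured for engraftment assay" (Section 6.2.4), so the 0H swab is a pre-dose reading. Section 1.2 schedules the post-dose swabs at 6H (±2 h), 24H (±2 h), 48H (±2 h), Day 7 and Day 28. The only post-dose follicular strip is at 24H. Each subject receives one application. Section 2.1 gives the next step: "we plan to expand the IND research to a Phase Ib multi-dosed study", provided the safety criteria are met.

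**The concern.** A schedule meant to hold a ratio above a threshold has to re-dose before the ratio falls through it. The example does the reverse: it takes a ratio already below 40% by 6 h and assigns an interval of 12 h. It is offered only as an illustration, but it is the sole guide to how a primary objective turns into a schedule, and it uses one of the two ratios that define engraftment.

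The sampling times raise a second question. The example names a 12 h interval, and no scheduled swab falls near 12 h. It therefore matters which swab results do and do not bear on that interval.

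At stake is the starting regimen of the planned multi-dosed study. Followed literally, the example would select an interval that the single-dose data argue against.

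**Working it through.** The plan gives no numerical basis for this objective (Section 10.2 states that no sample size or power estimate is made), so there is no figure to reproduce. The check is interval arithmetic, followed by a sensitivity analysis on an assumed model.

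**Inputs.** Threshold 40% and example rule: Sections 3 and 4.2. Pre-dose 0H swab: Sections 6.1.1 and 6.2.4. Swab windows: Sections 1.2 and 8.1. One application: Section 6.1.1. Densities for facial skin: Section 4.3. The ratio just after dosing and its rate of fall are not in the documents.

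**Step 1: the example against the aim, single dose.** If the ratio crosses 40% at time T and does not recover, hours below in the first 12 h = 12 − T.

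- T = 6 h: 12 − 6 = 6 h (50%)
- T = 4 h: 12 − 4 = 8 h (67%)
- T = 2 h: 12 − 2 = 10 h (83%)

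The example's condition is T ≤ 6 h, so 6 h is the minimum for the first interval. The visit window softens this in practice. A 6H swab taken late, at 8 h, and found below 40% guarantees only 12 − 8 = 4 h (33%).

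**Step 2: what the swabs can show.** The latest 6H swab is at 8 h and the earliest 24H swab at 22 h, so 22 − 8 = 14 h has no scheduled swab (nominally 24 − 6 = 18 h). Assuming a single downward crossing:

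| 6H | 24H | Reading for dosing every 12 h |
|---|---|---|
| below 40% | below 40% | argues against it on single-dose data |
| above 40% | below 40% | undecided: the crossing may be before or after 12 h |
| above 40% | above 40% | enough, but once daily is then supported too |

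Only the middle row is open, and the plan gives no rule for it.

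**Step 3: could carry-over rescue the example?** Assume constant resident load, first-order loss of product, no deoR signal from residents, and a single-dose crossing at 6 h. Let p0 be the ratio just after the first dose and r0 = p0/(1 − p0). A ratio of 40% is product/resident = 2/3. Then k = ln(1.5·r0)/6, the steady-state factor is S = 1/(1 − exp(−12k)), and hours below per 12 h interval = 12 − ln(1.5·r0·S)/k, or zero if negative.

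For p0 = 60%: r0 = 1.5, k = ln(2.25)/6 = 0.135, S = 1/(1 − 0.198) = 1.246, crossing at ln(2.804)/0.135 = 7.63 h, so 12 − 7.63 = 4.37 h below.

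| p0 | Hours below 40% per 12 h, steady state |
|---|---|
| 50% | 0 (trough 44%) |
| 55% | 2.5 |
| 60% | 4.4 |
| 70% | 5.6 |
| 80% | 5.9 |
| 90% | 6.0 |

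The shortfall vanishes when p0 is about 51.9% or less. This is not an idle case. Section 4.3 describes the Cohort 1 dose of 10^5 CFU/cm² as the "average within the range of normal bacterial concentration for facial skin", and a dose equal to resident load gives p0 = 10^5/(10^5 + 10^5) = 50%. In the model, that subject is below 40% for 6 h in the first interval, about 0.6 h in the second and not at all from the third. If benzoyl peroxide had reduced residents to 10^4, p0 would be 10^5/(1.1 × 10^5) = 91%, and carry-over would help hardly at all.

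**The case against.** The strongest reply is that the sentence is an illustration. It opens as an example, the surrounding text says only that the data will help to choose a regimen, no subject here is dosed by it, and a separate protocol will set the multi-dose schedule. That stands and limits the consequence. It does not make the example consistent with the aim stated just before it.

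A second reply is that twice daily may be the most frequent dosing that is practical for a topical product. That is plausible, but the text gives a different reason, namely staying above 40%.

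A reader might go further in three ways that the documents do not support.

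- *That 12-hourly dosing leaves half of every interval below threshold.* Step 1 is certain for the first interval only. Under repeat dosing with a 6 h crossing, the modelled shortfall runs from 0 to 6 h, and this trial cannot say where in that range it lies.
- *That the trial cannot show whether 12-hourly dosing would work.* That holds only for above at 6H and below at 24H. The other patterns do bear on the question.
- *That a probability can be put on the undecided pattern.* The chance that the crossing came before 12 h is 6/18 = 33% if crossing times are uniform over 6-24 h and ln 2/ln 4 = 50% if log-uniform. With no decay data, neither assumption has support, and in principle the answer is anywhere from 0 to 100%.

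The single-crossing assumption is also open to challenge. NB01 is a live culture that might regrow, and each swab samples a different quarter of the face (Section 8.1), so differences between visits are mixed with differences between quarters.

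**Conclusion.** The example in Sections 3 and 4.2 is wrong as written. On single-dose data it leaves at least 6 of the first 12 h below the threshold it is meant to maintain, if the ratio does not recover after crossing. Carry-over might reduce or remove that shortfall, and a single-application trial cannot measure it. Separately, given a single downward crossing, a result above 40% at 6H and below at 24H leaves 12-hourly dosing undecided. Below at 6H argues against it, and above at 24H supports once daily.

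This is a minor point: a wording error in the rule for a primary objective, with no effect on the dosing or safety of subjects in this trial. Nor does it follow that the sampling schedule must change. The later study could take a pre-dose swab at 12 h and observe the repeat-dose trough directly, which a single-dose swab here could not.

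**What to change.** Replace the example in both sections with text such as:

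> A schedule is supported only if both deoR/PanBac and Cas5/PanBac are still above 40% at the end of its dosing interval. Both above 40% at 24H supports once daily. Either below 40% at 6H means Q12 hours is not shown to keep levels above 40% on single-dose data. Both above at 6H but either below at 24H leaves Q12 hours undecided. Carry-over from repeat dosing is not measured in this study.

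If twice daily is intended as a practical ceiling, say that in place of the statement that levels will remain above 40%.

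The cost is a few sentences in Sections 3 and 4.2, with no new visit, swab or assay.

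A swab at about 12 h is an option, not a requirement. It would speak directly to the undecided pattern and falls before washing resumes at 24H. It would add about 10 swabs and assays, usually out of clinic hours. It would also be a fifth post-dose sample by Day 7 on a face divided into four quarters, so one quarter would be sampled twice by then. It would not measure carry-over.
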